## 2.3 Research question 3 (health system factors)

For assessing factors related to strengthening service delivery, measures will be used from the CSPS checklist and N-M and ASBC survey datasets. In the context of the overall evaluation, outcomes under this RQ3 count as secondary outcomes.

Table 4: Outcome measures for RQ3

Outcome	Indicator	Data source
Equipment and materials to support maternal nutrition services	
 
- % CSPS with maternal nutrition counseling job aids
 
- % CSPS with IFA supplementation job aid
 
- % CSPS with breastfeeding counseling job aids
 
- % CSPS with functional weighing scale
 
- % CSPS with currently stocked with IFA tablets
 
- % CSPS with register to monitor IFA stocks
 
- % CSPS reporting stock-out of IFA in past 6 months
 
	CSPS checklist
Service providers' training and supportive supervision	
 
- % NM received maternal nutrition training
 
- % ASBC received maternal nutrition training
 
	N-M survey ASBC survey

	
 
- % NM/ASBC by training content
 
- % NM/ASBC received supervision
 
- % NM/ASBC by supervision content
 
	
Service providers' knowledge	
 
- Knowledge scores for dietary diversity, adequate intake, IFA, and weight gain monitoring
 
- Knowledge scores for breastfeeding
 
	N-M survey ASBC survey
Service providers' work tasks and workload perceptions	
 
- % NM/ASBC record-keeping on ANC services
 
- % NM/ASBC by content of record-keeping
 
- % NM/ASBC with increased workload in past 1y due to ANC services
 
	N-M survey ASBC survey
Service providers' provision of services	
 
- % NM/ASBC provided maternal nutrition interventions
 
- % NM/ASBC by counseling messages provided (on dietary diversity, IFA, weight gain monitoring, and breastfeeding)
 
- % NM/ASBC used job aids for maternal nutrition counseling
 
- % ASBC provided home visits to PW/number of visits in last 30 days
 
- % ASBC conducted GASPA for PW/number of meetings in last 30 days
 
	N-M survey ASBC survey

### III. Statistical Analysis Plan

#### 3.1 General principles and methods

Data analyses will be performed using STATA version 16.0 (StataCorp LLC). All applicable statistical tests will be two-sided to allow potential findings of unexpected effects. Statistical significance will be presented at levels of  $p<0.05$ ,  $p<0.01$ , and  $p<0.001$ .

A diagram presenting the flow of clusters and individuals through the trial, based on the Consolidation Standard of Reporting Trials (CONSORT) statement: extension to cluster randomized trials (Campbell et al., 2012; Eldridge et al., 2016), is shown as follows.

[figure not shown]

Figure 1. CONSORT flow diagram for repeated cross-sectional surveys

### 3.2 Sample characteristics

Baseline and endline characteristics will be reported between randomized program groups (A&T and control). For household samples, indicators of maternal characteristics (age, marital status, education, occupation, and religion), obstetric history (age of marriage, age at first birth, gravida, parity, number of living children, and trimester of pregnancy,), household composition (size, number of adults and children, and household head) and other household characteristics (household food security, livelihood, and socioeconomic status) will be reported. Binary variables will be summarized as proportions, and continuous variables will be summarized as mean values with standard deviations (when normally distributed) or as median with interquartile range (for non-normal distribution variables). The Shapiro-Wilks test will be used to test for normality of data distribution. T-test will be used to compare and infer significant difference between the program groups.

Table 5: Dummy table for sample characteristics

Indicator	Baseline		Endline	
	A&T (N=)	Control (N=)	A&T (N=)	Control (N=)
	Mean (SD)	Mean (SD)	Mean (SD)	Mean (SD)
Age of respondent (years)				
	Percent	Percent	Percent	Percent
Marital status				
Education level				
Occupation				
Religion				

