1.3 Trial design

The present study is designed as a two-arm cluster-randomized, non-masked trial, consisting of two cross-sectional surveys at baseline and endline. The unit of randomization is the health and social promotion center (CSPS) catchment area. The study is designed to have sufficient power to estimate differences between study groups across regions (**Figure 1**). A baseline cluster/facility-level and household survey will take place in November-December 2019. As soon as the baseline survey is completed, the intervention will be implemented at the CSPS and in the villages of the intervention group for up to 12 months. The endline survey will take place approximately one year later in January-February 2021. The repeated cross-sectional study design will allow us to assess the impact of the maternal nutrition interventions on currently pregnant and recently delivered women.

Figure 1. Trial flow

[figure not shown]
Note: CSPS: Centre de Santé et de Promotion Social. The baseline and endline surveys will include cross-sectional interviews of pregnant, and recently delivered women and their husbands, as well as providers of ANC services.

II. Methods: Participants, Interventions and Outcomes

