3.1 Allocation

We applied stratified random allocation to obtain a more balanced distribution of cluster-level covariates between study arms. First, we divided clusters/CSPS by health districts. Then we stratified clusters into 2 strata using available data on a set of criteria:

- Type of catchment area
- Number of villages covered
- Total population size
- Total number of pregnant women and total number of children <6 months
- Number of ANC admissions and proportion of ANC attended
- Distance between CSPS and district hospital

Then we used Stata to assign unique computer-generated random numbers to each cluster, sort numbers, and allocate each cluster in order to one of two study arms (intervention or control).

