4.4 Statistical methods

Descriptive analyses will be used to describe characteristics of the two groups. Testing of differences between the two groups will be done using a random effects regression, accounting for the clustering of errors within and across health center catchment areas.

The randomized study design allows for the identification of causal effects of the maternal nutrition intervention through comparisons of mean outcomes between the treatment and control groups. Key indicators will include dietary diversity (among pregnant women), IFA consumption, weight gain monitoring, and breastfeeding practices (early initiation and exclusive breastfeeding). Impacts will be assessed using difference-in-difference (DID) estimation. Data management, data cleaning and statistical analyses will be conducted using Stata version 15 (Statacorp, USA).

V. Methods: Monitoring

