### 3.3 Impact estimates

The main analysis of impacts will be performed using intent-to-treat (ITT) specifications, wherein all study participants in the originally assigned program group at baseline are included in the statistical analysis and analyzed according to their program group, regardless of whether they received interventions or not. Women who refused or withdrew consent or those who are ineligible according to study protocol are excluded from ITT analysis.

The main impacts of the interventions will be estimated for: (1) maternal diet during pregnancy, (2) consumption of IFA supplements, and (3) early breastfeeding practices; secondarily, impact will be estimated for exposure to key interventions: (4) maternal nutrition counseling, (5) counseling on IFA supplementation, (6) weight gain monitoring and counseling, (7) breastfeeding counseling. The impact on dietary diversity will be assessed among PW, and impact on all the remaining outcomes will be assessed among RDW.

The difference-in-difference (DID) method will be used to estimate impacts by comparing the changes in outcomes over time (baseline vs. endline) between study arms (intervention vs. control). Point estimates and changes in the outcomes will be reported. For the analysis, the Stata *diff* command will be used, accounting for clustering at the CSPS level with a cluster version of Huber-White robust estimator of standard errors and using degrees of freedom appropriate for the number of CSPS (Hayes & Moulton, 2017). The fixed effects in the two-level regression models will be study arm, survey time, and arm times survey; the latter estimates the difference between arms in changes over surveys. We will conduct ITT analyses based on the original evaluation design, as well as the adjusted ITT analyses using the ITT groups but adjusting for gestational age (for PW only), maternal characteristics, child age and sex (for RDW only), and other variables that may be different between study arms.

Table 6: Dummy table for impact estimates

Indicator	Baseline		Endline		Unadjusted DID	Adjusted DID
	A&T (N=)	Control (N=)	A&T (N=)	Control (N=)		
	Mean (SD)	Mean (SD)	Mean (SD)	Mean (SD)	pp	pp
Dietary diversity score (number of food groups)						
Number of IFA tablets consumed						

	Percent	Percent	Percent	Percent	
Minimum dietary diversity ( $\geq 5$ food groups)					
Consumed 180+ IFA tablets					

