#### 3.4.2. Analysis of program impact pathways

The program impact pathway (PIP) was developed in collaboration with the A&T program team to map out the mechanisms through which the interventions were expected to achieve impact. The purpose of

the PIP analysis is to lay out the theoretical causal links between program activities, outcomes, and impacts. We will examine key indicators along the components of pathways (addressed in part by RQ2 and RQ3), to interpret and support the impact evaluation results. We will compare differences between program groups for indicators along the pathway matched to the relevant outcomes (dietary diversity, IFA consumption, and breastfeeding practices), using mixed-effects regression models, accounting for geographic clustering. Additional path analyses will be considered based on the results of the above analyses.

Table 7: Measures for program impact pathways

Outcome	Key Indicators	Data source
Service providers' capacity-building and service provision:		
Training and supervision (RQ3)	
 
- % NM received maternal nutrition training
 
- % ASBC received maternal nutrition training
 
- % NM/ASBC by training content
 
- % NM/ASBC received supervision
 
- % NM/ASBC by supervision content
 
	N-M survey ASBC survey
Service providers' knowledge (RQ3)	
 
- Knowledge scores for dietary diversity, adequate intake, IFA, and weight gain monitoring
 
- Knowledge scores for breastfeeding
 
	N-M survey ASBC survey
Service provision (RQ3)	
 
- % NM/ASBC provided maternal nutrition interventions
 
- % NM/ASBC by counseling messages provided (on dietary diversity, IFA, weight gain monitoring, and breastfeeding)
 
- % NM/ASBC used job aids for maternal nutrition counseling
 
- % ASBC provided home visits to PW/number of visits in last 30 days
 
- % ASBC conducted GASPA for PW/number of meetings in last 30 days
 
	N-M survey ASBC survey
Beneficiaries' exposure and behavioral determinants:		

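### SAP 3.2 tests arm differences in sample characteristics with a t-test that makes no stated allowance for clustering by CSPS, contrary to Protocol 4.4

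*SAP*

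**What the plan says.** SAP 3.2 covers maternal, obstetric and household characteristics at baseline and endline. After the summary statistics and a normality test, it states: "T-test will be used to compare and infer significant difference between the program groups". It does not say whether the test is run on women or on CSPS means. SAP 3.1 sets no general clustering rule that would fill the gap. It does say that significance will be shown at three levels, down to p<0.001.

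Other parts of the plan allow for clustering:

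- Protocol 1.3: "The unit of randomization is the health and social promotion center (CSPS) catchment area".
- Protocol 4.4, directly after its sentence on describing the two groups: "Testing of differences between the two groups will be done using a random effects regression, accounting for the clustering of errors".
- SAP 3.3, for the impact estimates: "accounting for clustering at the CSPS level with a cluster version of Huber-White robust estimator of standard errors".
- SAP 3.4.2, for the pathway indicators: "using mixed-effects regression models, accounting for geographic clustering".

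SAP 3.3 also adjusts for gestational age, maternal characteristics, child age and sex, "and other variables that may be different between study arms". It does not say how those further variables will be identified.

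**The concern.** Women in the same CSPS catchment area tend to resemble each other in religion, occupation, education and wealth. An ordinary two-sample t-test treats them as independent. When whole catchment areas are randomised, its standard error is too small by the square root of the design effect, and it rejects more often than its stated level even when allocation worked perfectly.

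The characteristics table is where readers judge whether the arms are comparable. Each survey draws different women, so that judgement is made twice. An over-sensitive test could make a sound randomisation look flawed.

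There is one possible route into the results. If analysts used the 3.2 tests to choose the open-ended extra covariates in SAP 3.3, the false flags would shape the adjusted estimate. The SAP neither states nor excludes this.

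**Working it through.** The plan gives no error rate for this table, so there is no figure to reproduce first.

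**Inputs**

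- Clusters: 40 CSPS per arm (SAP 1.2).
- Sample per survey: 480 pregnant women (PW) and 960 recently delivered women (RDW) per arm (Protocol 2.5, SAP 1.3). Women per CSPS: m = 480/40 = 12 (PW) and 960/40 = 24 (RDW).
- ICC: none is given for any characteristic, so 0.01, 0.02 and 0.05 are assumed. The outcome ICCs in Protocol 2.5 (0.110 for dietary diversity, 0.206 for IFA tablets) serve only as an upper illustration.
- Two-sided tests (SAP 3.1).

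**Formula**

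Design effect DE = 1 + (m − 1) × ICC. The actual error rate of the unclustered test at nominal level α is 2 × [1 − Φ(z / √DE)], where z is the two-sided critical value.

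Example, RDW at ICC 0.05: DE = 1 + 23 × 0.05 = 2.15; √DE = 1.47; 1.96/1.466 = 1.337; actual rate 18.1%.

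| Sample | ICC | DE | SE too small by factor | Actual rate at nominal 5% | Actual rate at nominal 0.1% |
|---|---|---|---|---|---|
| PW | 0.01 | 1.11 | 1.05 | 6.3% | 0.18% |
| PW | 0.02 | 1.22 | 1.10 | 7.6% | 0.29% |
| PW | 0.05 | 1.55 | 1.24 | 11.5% | 0.82% |
| PW | 0.110 (outcome) | 2.21 | 1.49 | 18.7% | 2.7% |
| RDW | 0.01 | 1.23 | 1.11 | 7.7% | 0.30% |
| RDW | 0.02 | 1.46 | 1.21 | 10.5% | 0.65% |
| RDW | 0.05 | 2.15 | 1.47 | 18.1% | 2.5% |
| RDW | 0.206 (outcome) | 5.74 | 2.40 | 41.3% | 17% |

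At ICC 0 the test is correct.

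**Check by simulation**

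With 10,000 runs and 40 clusters per arm, the unclustered t-test rejected in 18.6% of runs (PW, ICC 0.110) and 40.9% (RDW, ICC 0.206), in line with the formula. Across the ICCs simulated (0.01 to the outcome values), a t-test on CSPS means rejected in 4.6% to 5.3%.

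**Effect of stratified allocation**

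Protocol 3.1 divides CSPS by health district and then into two strata. With four districts, the simulation assumes eight equal strata of five CSPS per arm. The share of between-CSPS variance that the strata explain is also assumed. Rejection at nominal 5% by the unclustered t-test (4,000 runs per scenario, Monte Carlo error about 0.4 to 0.8 percentage points):

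| Sample, ICC | Strata explain 0% | 25% | 50% |
|---|---|---|---|
| PW, 0.01 | 6.5% | 6.0% | 5.3% |
| PW, 0.05 | 11.6% | 9.1% | 8.0% |
| PW, 0.110 | 18.9% | 15.7% | 12.3% |
| RDW, 0.01 | 7.6% | 6.5% | 6.9% |
| RDW, 0.05 | 17.5% | 15.1% | 11.1% |
| RDW, 0.206 | 41.3% | 35.7% | 28.1% |

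Stratification reduces the inflation but does not remove it, except where the ICC is very small. A t-test on CSPS means in the same runs rejected in 1.9% to 5.2%.

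**The case against.** The strongest reply is that nothing answering the main research questions depends on this table. The impact estimates use CSPS-clustered standard errors and are reported both unadjusted and adjusted. Dummy Table 5 has no p-value column, so readers can compare the means and percentages themselves. An over-sensitive test exaggerates chance imbalance rather than hiding it. All of this is right, and it limits the point to the description of balance.

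SAP 3.2 also does not state the level of the test, and a t-test on CSPS means would be valid. But the section lists respondents' characteristics, and its dummy table reports N, SD and percentages by arm with no mention of cluster means. If a cluster-level test is intended, the SAP still has to say so.

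The ICCs are assumed, and the outcome ICCs are no evidence about age or religion. This stands, and is why the range 0.01 to 0.05 carries the weight. Protocol 2.6 speaks of at least 10 households per cluster for PW. With m = 10 the PW rates at ICC 0.01, 0.02 and 0.05 are 6.0%, 7.1% and 10.4%, so little changes.

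The use of these tests to pick covariates is only a possibility. That also stands.

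Finally, a clustered test that ignores the strata is conservative when strata matter. For RDW, with strata explaining 25% or 50% of the between-CSPS variance, clustered standard errors without strata terms gave 3.6% or 2.7% at ICC 0.05, and 3.4% or 1.6% at ICC 0.206. With strata terms the rate returns to about 5%. This refines the remedy and does not defend the unclustered test.

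**Conclusion.** The concern holds. SAP 3.2 departs from Protocol 4.4, and followed as written it understates standard errors for characteristics that cluster by CSPS. Without strata effects, and for ICCs of 0.01 to 0.05, a nominal 5% test has an actual rate of 6.3% to 11.5% (PW) and 7.7% to 18.1% (RDW). At the 0.1% level the rates are 0.18% to 0.82% and 0.30% to 2.5%. If strata explain half of the between-CSPS variance, the 5% rates at ICC 0.05 fall to about 8% and 11%.

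These figures rest on an individual-level reading of the t-test, equal cluster sizes and assumed ICCs. The damage is to the reported picture of balance. The type I error of the primary tests is not directly affected. It should be fixed because the departure is clear and the correction is nearly free.

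**What to change.** In SAP 3.2, replace the t-test with the comparison in Protocol 4.4: a regression on arm with a CSPS random effect, or with CSPS-clustered standard errors. Including the allocation strata would keep the test close to its nominal level. Alternatively, report standardised differences by arm and drop the p-values from this table.

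In SAP 3.3, add one sentence saying that the additional covariates of the adjusted difference-in-difference model are not chosen by the significance tests in 3.2. How that set is chosen still has to be specified separately.

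The cost is two sentences of SAP text and a changed Stata command. No further data are needed.

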### 3.3 Impact estimates

The main analysis of impacts will be performed using intent-to-treat (ITT) specifications, wherein all study participants in the originally assigned program group at baseline are included in the statistical analysis and analyzed according to their program group, regardless of whether they received interventions or not. Women who refused or withdrew consent or those who are ineligible according to study protocol are excluded from ITT analysis.

The main impacts of the interventions will be estimated for: (1) maternal diet during pregnancy, (2) consumption of IFA supplements, and (3) early breastfeeding practices; secondarily, impact will be estimated for exposure to key interventions: (4) maternal nutrition counseling, (5) counseling on IFA supplementation, (6) weight gain monitoring and counseling, (7) breastfeeding counseling. The impact on dietary diversity will be assessed among PW, and impact on all the remaining outcomes will be assessed among RDW.

The difference-in-difference (DID) method will be used to estimate impacts by comparing the changes in outcomes over time (baseline vs. endline) between study arms (intervention vs. control). Point estimates and changes in the outcomes will be reported. For the analysis, the Stata *diff* command will be used, accounting for clustering at the CSPS level with a cluster version of Huber-White robust estimator of standard errors and using degrees of freedom appropriate for the number of CSPS (Hayes & Moulton, 2017). The fixed effects in the two-level regression models will be study arm, survey time, and arm times survey; the latter estimates the difference between arms in changes over surveys. We will conduct ITT analyses based on the original evaluation design, as well as the adjusted ITT analyses using the ITT groups but adjusting for gestational age (for PW only), maternal characteristics, child age and sex (for RDW only), and other variables that may be different between study arms.

Table 6: Dummy table for impact estimates

Indicator	Baseline		Endline		Unadjusted DID	Adjusted DID
	A&T (N=)	Control (N=)	A&T (N=)	Control (N=)		
	Mean (SD)	Mean (SD)	Mean (SD)	Mean (SD)	pp	pp
Dietary diversity score (number of food groups)						
Number of IFA tablets consumed						

	Percent	Percent	Percent	Percent	
Minimum dietary diversity ( $\geq 5$ food groups)					
Consumed 180+ IFA tablets					

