2.5 Sample size

The two main samples for the primary outcomes are: 1) pregnant women (PW) as this sample allows the assessment of diet quality during pregnancy; and 2) recently delivered women (RDW) who have children under 6 months of age, as this sample provides the best opportunity to assess the primary outcome related to intervention exposure throughout pregnancy (i.e., IFA consumption). Based on an initial mean dietary diversity score of 3.52 food groups across both regions and intra-cluster correlation of 0.110 from the 2019 baseline data (Kim et al., 2020), a significance level of 5% and power of 80%, the sample size of 480 PW per arm is estimated to detect a difference of 0.37 in the mean dietary diversity score after intervention.

For RDW, using an initial mean of 108.64 IFA tablets consumed across both regions and intra-cluster correction of 0.206 at baseline (Kim et al., 2020) and the same assumptions above for statistical significance, the sample size of 960 RDW per arm is estimated to detect a difference of 15 tablets in the mean IFA tablets consumed after intervention. If husbands of RDW are present at the time of the survey, they will also be interviewed briefly about their health and nutrition knowledge and any support provided during pregnancy. Approximately half of the expected sample size of husbands was available at baseline.

Outside of these two main samples, nurses-midwives (1 per CSPA) and community health workers (within 3 villages per CSPA) will be interviewed. In addition, direct observations of ANC visits (2 per CSPA) to assess service quality, followed by exit interviews to assess client satisfaction, will be conducted among a subgroup of pregnant women attending ANC at the time of survey.

The overall study samples sizes are presented in **Table 2**.

Table 2: Estimated sample sizes

	Baseline 2019		Endline 2020	
	Intervention	Control	Intervention	Control
Pregnant women	480	480	480	480
Women with children 0-5 months old	960	960	960	960
Husbands of women with children 0-5 months old	960	960	960	960
Nurses-midwives	40	40	40	40
Community health worker (ASBCs)	120	120	120	120
ANC observation & exit interview	80	80	80	80
Total	2,640	2,640	2,640	2,640

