### 1.2 Impact evaluation study design

The impact evaluation of A&T's interventions used a cluster-randomized design with repeated cross-sectional surveys at baseline and endline. We applied stratified random allocation to 80 health centers (CSPS, Centre de Santé et de Promotion Social) within four health districts (Boromo, Toma, Dande, and Lena), which were assigned to either the A&T intervention (40 CSPS) or control areas (40 CSPS). The baseline survey was conducted in November-December 2019 and the endline survey was conducted in January-March 2021 in the same 80 CSPS catchment areas, thereby creating panel data at the CSPS level (not at individual level). Program implementation duration was approximately 12 months, with a couple of months of interruption due to the COVID-19 pandemic in March-April 2020.

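### SAP 3.3's difference-in-difference for both primary outcomes is valid but less precise than adjusting endline for the CSPS baseline mean: clearly so for diet, only conditionally for IFA

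*SAP*

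**What the plan says.** Protocol 4.4 names the method: "Impacts will be assessed using difference-in-difference (DID) estimation". SAP 3.3 repeats it: "The difference-in-difference (DID) method will be used to estimate impacts by comparing the changes in outcomes over time". It then gives the model: "The fixed effects in the two-level regression models will be study arm, survey time, and arm times survey". The impact estimate is the arm-by-survey coefficient, with CSPS-robust standard errors. The arm main effect is left free, so the baseline difference between arms is estimated and fully subtracted.

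SAP 3.3 also plans an adjusted analysis, "adjusting for gestational age (for PW only), maternal characteristics, child age and sex (for RDW only"), plus further variables that may differ between arms. The CSPS baseline mean of the outcome is not listed. SAP Table 6 reports an unadjusted and an adjusted DID for both primary outcomes.

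On the data available, SAP 1.2 says "the endline survey was conducted in January-March 2021 in the same 80 CSPS catchment areas". The same section draws the consequence for the structure of the data: "thereby creating panel data at the CSPS level (not at individual level"). The women differ between surveys, but every CSPS has a baseline mean for each primary outcome.

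**The concern.** Allocation of CSPS was random (Protocol 3.1), so the expected baseline difference between arms is zero and any observed difference is chance: part stable difference between CSPS, part sampling noise from 12 or 24 women per CSPS. The DID removes all of it with weight 1, noise included. When baseline CSPS means predict endline means poorly, this adds more variance than it takes away. An endline regression on arm plus the CSPS baseline mean uses the same data and lets them set the weight.

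At stake is the width of the confidence intervals for the two primary outcomes, which may be wider than the collected data require.

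**Working it through.** **Inputs.** Protocol 2.5 gives "intra-cluster correlation of 0.110 from the 2019 baseline data" for diet and "intra-cluster correction of 0.206 at baseline" for IFA (read as correlation). Women per CSPS per survey: 480/40 = 12 pregnant women and 960/40 = 24 recently delivered women. K = 80 CSPS, 40 per arm. The CAC (the correlation over time of true CSPS levels) is not given, so its full range from 0 to 1 is shown as an assumption.

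**The plan's own figures.** Design effects DE = 1 + (m-1)ICC are 1 + 11(0.110) = 2.21 and 1 + 23(0.206) = 5.738. No SD is given, so 480 and 960 per arm cannot be reproduced directly. Solving back for an endline-only comparison (two-sided 5%, 80% power), SD = d/[2.80 x sqrt(2DE/N)], gives about 1.38 food groups and 49.0 tablets. Under a DID the implied SD runs from 0.97 (CAC 0) to 1.53 (CAC 1) for diet and from 34.6 to 93.1 for IFA. The stated sizes are neither confirmed nor refuted. The variance cuts below do not depend on the SD.

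**Variance comparison, equal variances and cluster sizes.** The correlation of baseline and endline CSPS means is r = CAC x m x ICC/DE. Var(DID) is proportional to 2(1-r). Var(adjusted) is proportional to (1-r²)(K-3)/(K-4), where the last factor, 77/76, is the price of estimating the slope. Hence cut = 1 - [(1+r)/2](77/76).

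| CAC | r, diet | cut, diet | r, IFA | cut, IFA |
|---|---|---|---|---|
| 0 | 0 | 49.3% | 0 | 49.3% |
| 0.5 | 0.299 | 34.2% | 0.431 | 27.5% |
| 0.8 | 0.478 | 25.1% | 0.689 | 14.4% |
| 1 | 0.597 | 19.1% | 0.862 | 5.7% |

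Simulation with 80 CSPS agrees within about 1 percentage point. Both estimators were unbiased, with type I error of 4.8-5.2%. Intervals narrow by about 29/19/13.5/10% (diet) and 29/15/7.5/3% (IFA). With the 10 pregnant women per cluster of Protocol 2.6, the diet cut at CAC 1 would be 21%.

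**What the CAC 0 figure means.** There the adjusted estimate is about 1% worse than a plain endline comparison, so the 49% is not a gain from using baseline. With equal variances the DID has larger variance than plain endline whenever r < 0.5, that is CAC below 0.5/0.597 = 0.84 (diet) or 0.5/0.862 = 0.58 (IFA).

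**Unequal variances.** With endline/baseline variance ratio v, Var(adjusted)/Var(DID) = (77/76) v(1-r²)/(1+v-2r√v). At CAC 0/0.5/0.8/1:
- v = 1.4: cuts of 41/24/14/8% (diet) and 41/16/3/-1% (IFA).
- v = 0.7: cuts of 58/46/39/35% (diet) and 58/41/32/29% (IFA).

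**Individual covariates.** The table has no covariates in either model. Assume, for illustration, that covariates explain 10% of within-CSPS variance, with total variance 1, at CAC 1. Each variance below is on the same scale, per CSPS.
- Adjusted DID: 2 x 0.9(1-ICC)/m = 0.1335 (diet), 0.0596 (IFA).
- Endline on arm plus CSPS baseline mean, no covariates: (DE/m)(1-r²)(77/76) = 0.1200 and 0.0624. The diet cut drops to 10%, and for IFA the adjusted DID is about 5% more precise.
- The same covariates in both models, raw baseline mean: [ICC + 0.9(1-ICC)/m - ICC²/(DE/m)](77/76) = 0.1125 and 0.0591, cuts of 16% and 1%.
- The same, but with the baseline mean also covariate-adjusted (replace DE/m by ICC + 0.9(1-ICC)/m): cuts of 18% and 5%.

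At CAC 0 the like-for-like cut stays 49%.

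**Can the SAP's adjusted DID recover the gain?** No. With equal cluster sizes, adding a covariate that is constant over time within CSPS to the stacked model leaves the arm-by-survey estimate unchanged.

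**The case against.** Nothing in the plan is wrong: protocol and SAP agree on a DID, which is a recognised estimator for this design. It also has a merit that adjustment lacks. If stable CSPS levels happen to be imbalanced, the DID removes the imbalance fully, whereas at CAC 1 the adjusted model leaves 1 - 0.597 = 40% of it for diet and 14% for IFA. That is true of a given allocation. Over randomisations both estimators are unbiased, and the adjusted one usually has the smaller variance.

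The size of the gain rests on two quantities that the documents do not give. This stands, and for IFA it is decisive: at high CAC the gain is small and can vanish. A comparison with the unadjusted DID alone would also flatter a model that drops the SAP's individual covariates. That stands too, and is why the fix pairs like with like.

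Finally, SAP 1.2 describes the endline survey in the past tense, so a new primary estimator could look like selective choice. The documents do not show whether results by arm had been seen. The objection limits when the change may be made; it does not remove the case for it.

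A reader might infer that the DID is biased, or that the trial is underpowered. Neither follows: randomisation makes both estimators unbiased, and without an SD or a CAC the documents cannot show a power shortfall.

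**Conclusion.** The point holds as an inexpensive gain in precision for a valid plan. For diet, the like-for-like variance cut is about 19% to 49% over CAC 1 to 0, given 80 CSPS, equal variances and equal cluster sizes. It falls to about 8% at CAC 1 if endline variance is 1.4 times baseline. For IFA the corresponding range is about 6% to 49%, but a material gain cannot be promised: it is nil or about -1% at CAC 1 with that variance ratio. The lower ends also slip somewhat when covariates are in both models.

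It would be too strong to read the 49% as the value of the baseline data, or to say that adjustment always beats the DID. Two other simplifications do not inflate the range. With cluster sizes varying (assumed CV 0.3), simulated cuts at CAC 0/0.5/0.8/1 were 50/35/29/25% (diet) and 49/31/26/35% (IFA). With eight assumed strata explaining half of the stable CSPS variance, they were 49/40/32/26% and 49/34/21/9%.

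**What to change.** In SAP 3.3, make the primary estimator for each primary outcome a linear regression of the endline woman-level outcome on arm plus the CSPS baseline mean of that outcome, with CSPS-robust standard errors and t degrees of freedom based on the number of CSPS. Fit it once without and once with the individual covariates of the adjusted DID, so that each Table 6 column has a like-for-like counterpart, and name in advance which version is primary. The SAP's covariate list is open-ended and must be closed first. In the covariate version, consider taking the CSPS baseline mean from the covariate-adjusted baseline outcome, which keeps more of the gain.

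Record this as a dated change from Protocol 4.4 before any endline comparison by arm, and report the unadjusted and adjusted DID beside it. If results by arm have already been seen, keep the DID primary and report the new estimate as supplementary.

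The cost is a few lines of code and extra columns in Table 6, with no new data or participants. The real price is a documented departure from the protocol's named estimator after endline fieldwork, which the dating rule and the retained DID are there to contain.
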